7.5.2.2 Tumour shrinkage

Tumour shrinkage for each patient, measured (via central imaging review) as the maximum decrease from baseline (i.e. minimum sum of target lesion diameters after randomisation minus baseline), will be compared for the two treatment groups. An analysis of covariance (ANCOVA) for the minimum sum of diameters, with the baseline sum of diameters fitted as a covariate and the randomisation strata fitted as factors will be performed.

In addition waterfall plots of the maximum percentage reduction from baseline sum of target lesion diameters will be presented for each treatment group.

7.5.2.3 Patient-reported Outcomes

HRQOL questionnaires as measured by the EORTC QLQ-C30 and QLQ-LC13 at baseline, during treatment and follow-up will be included in the analysis. All scoring of the symptom scales/items will follow the EORTC scoring algorithm.

The analyses will focus on cough, dyspnea and pain; specifically:

- Cough: Q31 - How much did you cough? (QLQ-LC13)
- Dyspnoea: Composite of: Q33 - Were you short of breath when you rested? Q34 - Were you short of breath when you walked? Q35 - Were you short of breath when you climbed stairs? (QLQ-LC13). Individual item from QLQ-C30, Q8 - Were you short of breath?
- Pain: Composite of: Q9 - Have you had pain? Q19 - Did pain interfere with your daily activities? (QLQ-C30). Individual items from QLQ-LC13, Q40 - Have you had pain in your chest? Q41 - Have you had pain in your arm or shoulder? Q42 - Have you had pain in other parts of your body?

For each of the summary scales and items measuring the above the treatment groups will be compared for the following:

Distribution of patients improved, stable or worsened

Improvement will be defined as a score that improves from baseline by at least 10 points (on the 0-100 point scale) at anytime during the study. If a patient has not improved, worsening will be defined as a 10 point worsening at anytime during the study. Otherwise, a patient will be considered as stable.

The number and percentage of patients falling into each of these three categories will be summarised by treatment group. All randomized patients will be included in the denominator. A logistic regression model, stratified by stratification factor race will be used

to compare the distribution of patients improving/not improving across the two treatment groups.

Time to deterioration

Time to deterioration (months) is defined as the time from randomisation to an increase (worsening) from the baseline score of at least 10 points on the 0-100 point scale. Patients who die before deteriorating and before the end of follow-up will be analysed as having deteriorated at the time of death. Disease progression without scale deterioration will be censored at the time of the last scale measurement. Patients with no HRQoL assessments will be censored at day of randomisation. Patients who are alive with no disease progression and no scale deterioration at the end of the follow-up will be censored at the date of last questionnaire.

This time to event data will be analysed and summarised using the same methodology as for the primary efficacy endpoint, refer to [Section 7.4](#). The hazard ratios will be displayed using Forest plots.

Change in scores over time

Changes in scores over time will be assessed using longitudinal models; these will be mixed-effects growth curve models with the average profile over time for each endpoint described by a piecewise linear model adjusted for the fixed effects race. The models will allow the slope to change at 8, 12, and 16 weeks. Each model will also include the two random effects of intercept and slope (time from randomisation). The area under the estimated growth curve (AUC) up to the median follow-up time will be calculated as a summary measure for each treatment group; this will be divided by the median follow-up time so that it can be interpreted as the mean HRQOL score up to the median follow-up time. The treatment effect will be estimated as the average difference between the treatment group means scores, together with a 95% confidence interval and associated p-value based on a t-statistic with degrees of freedom calculated using the Kenward-Roger method. The results of the analyses will be displayed using Forest plots.

In addition, all single items and subscales (functional and symptom) from both questionnaires will be analysed in a similar fashion to summarise the impact of therapy over the entire profile of the measures, and to examine the consistency of component items with the composite measures.

Note as higher scores represent a 'better' level of functioning; deterioration in scales/items related to functioning will be defined as a decrease from baseline score of at least 10 points.

Finally, the usage of cough, dyspnoea and pain medication will be described.

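### The HRQoL improved/stable/worsened table makes 'stable' the default, so randomised patients with no usable change score are reported as having stable symptoms

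*SAP*

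**What the plan says.** SAP section 7.5.2.3, under the distribution of patients improved, stable or worsened, sets these rules for each cough, dyspnoea and pain scale or item:

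- Improved, judged over the whole trial: "Improvement will be defined as a score that improves from baseline by at least 10 points (on the 0-100 point scale) at anytime during the" …
- Worsened: "If a patient has not improved, worsening will be defined as a 10 point worsening at anytime during the study".
- Stable: "Otherwise, a patient will be considered as stable".
- Reporting: "The number and percentage of patients falling into each of these three categories will be summarised by treatment group".
- Denominator: "All randomized patients will be included in the denominator".
- Test: a logistic regression stratified by race, "to compare the distribution of patients improving/not improving across the two treatment groups".

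The time-to-deterioration analysis in the same section does name the patients at issue. For deaths: "Patients who die before deteriorating and before the end of follow-up will be analysed as having deteriorated at the time of death". For patients without forms: "Patients with no HRQoL assessments will be censored at day of randomisation".

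Protocol section 7.3.2.1.4 defines only the proportion improved. The stable and worsened classes are an addition in the SAP.

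**The concern.** Improved and worsened can be assigned only to a patient with a baseline score and at least one later score. Stable has no such condition; it is whatever is left over. A patient about whom nothing is known after baseline, or who had no baseline, then enters the table as someone whose symptoms held steady.

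For the protocol's measure, the proportion improved, counting patients without data as not improved is conservative. Once the remainder is divided into stable and worsened, the same convention turns favourable, because absence of data is shown as symptom control. HRQoL is a named secondary endpoint, and SAP section 7.5.2.3 extends similar analyses to all items and subscales of both questionnaires, so the inflated row would recur across many scales. A reader of the report could not tell how much of 'stable' was observed.

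**Working it through.** **What the rule does.** The plan states no figure on this point, so the check is to trace each kind of randomised patient through the rule.

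| Patient | Improved? | Worsened? | Reported as |
|---|---|---|---|
| No baseline score | cannot be computed | cannot be computed | stable |
| Baseline, no post-baseline score | no | no | stable |
| Died before any evaluable post-baseline score | no | no | stable |
| Died after a recorded 10-point change | as recorded | as recorded | improved or worsened |
| Scores present, no 10-point change | no | no | stable (as intended) |

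The first three rows are the fault.

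**Effect on the table.** Let *u* be the share of an arm with no usable change score, and *s* the share with scores but no 10-point change, both out of all randomised.

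Reported stable = *s* + *u*.

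The improved and worsened shares do not contain *u*. Each percentage point of patients without usable scores adds one percentage point to stable and nothing elsewhere.

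To show the scale, assume that patients with scores split 40/30/30 into improved, worsened and stable. Neither this split nor the range of *u* comes from the documents.

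| *u* (assumed) | Observed stable, 0.30 × (1 − *u*) | Reported stable |
|---|---|---|
| 5% | 28.5% | 33.5% |
| 10% | 27.0% | 37.0% |
| 20% | 24.0% | 44.0% |
| 30% | 21.0% | 51.0% |

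**Early deaths, from the plan's own assumptions.** Inputs:

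- Median OS 7.00 months for erlotinib and 8.75 months for afatinib (Protocol section 7.6).
- 397 and 398 patients (Protocol synopsis).
- First scheduled post-baseline form at the start of course 2, with courses of 28 days (Protocol Flow Chart and its footnote 9).
- Exponential survival and 30.4375 days per month (assumptions).

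As a check on the survival inputs, 7.00/8.75 gives the stated hazard ratio of 0.80, and the Schoenfeld formula then gives 631 deaths for 80% power against the plan's 632.

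P(death by day *d*) = 1 − exp(−ln 2 × *d* / (median × 30.4375)).

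- Erlotinib, *d* = 28: 1 − exp(−0.6931 × 28 / 213.06) = 8.7%; × 397 ≈ 35 patients.
- Afatinib, *d* = 28: 1 − exp(−0.6931 × 28 / 266.33) = 7.0%; × 398 ≈ 28 patients.

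The visit window of −3 to +2 days corresponds to *d* between 25 and 30. Over that range the figures are 7.8% to 9.3% for erlotinib and 6.3% to 7.5% for afatinib.

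The between-arm difference at day 28 is 8.7% − 7.0% = 1.7 percentage points.

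**The case against.** The best defence is that the SAP's general conventions already cover these patients. Section 6.6 says that missing efficacy data will generally not be imputed. Section 7 takes percentages over all patients in the set, with or without values, and shows a missing row when values are missing. On that view an all-randomised denominator sits comfortably beside a missing row, and a patient with no change score would go there.

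This does not rescue the text. Section 6.6 gives a specific HRQoL rule only for time-to-event analyses. The missing row in section 7 appears only if a value is missing, and the specific rule in section 7.5.2.3 gives everyone a value and limits the table to three categories. Where a not-evaluable class was wanted, as for best RECIST response in section 7.5.2.1, the SAP names it. If the general convention was meant to apply here, one sentence must say so.

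Other limits do stand:

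- A reader might infer that everyone who died is called stable. That is not so: a death after a recorded 10-point change keeps its category.
- A reader might infer that worsened is understated. That follows only if death counts as symptom worsening, which nothing in the plan requires for this table. Time to deterioration must give death some status, as event or censoring; a table of recorded score changes asks a different question. The two rules differ but do not contradict each other.
- No combined improved-or-stable summary is planned, and the only test pools stable with worsened.
- The day-28 figures extrapolate medians to an early period in patients selected for ECOG 0 or 1. End-of-treatment and follow-up forms would give some of the early deaths a score.

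**Conclusion.** Wrong as written, but minor. Followed literally, SAP section 7.5.2.3 reports patients with no baseline score, no post-baseline score, or death before any evaluable post-baseline score as having stable symptoms.

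The damage is confined to the stable row of the descriptive distribution. The improved and worsened counts, the improved/not-improved regression, time to deterioration and the longitudinal models are unaffected, so the documents do not support reading this as a bias in any planned treatment comparison.

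The inflation equals the share of patients without a usable change score. That share cannot be computed from the documents, which give no rate for missing forms. The only component that can be sized is early death: about 35 erlotinib and 28 afatinib patients by day 28, given constant hazards at the planning medians, less any who complete an end-of-treatment form.

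**What to change.** Amend SAP section 7.5.2.3 as follows:

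1. Define stable as a baseline score and at least one post-baseline score, with no change of 10 points or more in either direction.
2. Add a fourth row, 'no evaluable change score', split into died and other.
3. Keep all randomised patients as the denominator, so that the four rows add to 100%.
4. Apply the same layout wherever the table is repeated for other items and subscales.

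The cost is a few words of SAP text, one extra table row with its split, and a smaller stable percentage. No new data are needed, and no test or other count changes.

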9. [EQ-5D](#), [EORTC QLQ-C30](#) and [EORTC QLQ LC-13](#) questionnaires will be completed at baseline and then (before seen by the investigator) at the start of course 2, 3, 4, and every 2nd course thereafter, EOT and FUP. After approval of Protocol Version 3.0, the collection of [EQ-5D](#), [EORTC QLQ-C30](#) and [EORTC QLQ LC-13](#) questionnaires will no longer be required.
10. See [Appendix 10.7](#): Adverse Event Reporting Process
12. Tumour assessments should include CT scans of the chest and abdomen and, if clinically indicated, imaging of any other known or suspected sites of disease (e.g. pelvis, brain) using an appropriate method (CT scan or MRI). See [Appendix 10.1](#) for lesion measurement specifications. Assessment will be performed at the following timepoints until progression or start of further treatment for disease. In the event of early discontinuation due to Adverse Events or an interruption/delay to treatment the tumour assessment schedule will not be changed.  
Screening Period (up to 21 days before randomization)  
During week 8 (56-64 days after randomization)

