#### 7.3.2.1.4 Patient-reported Outcomes

The analyses will focus on cough, dyspnea, and pain measured on the [EQ-5D](#), [EORTC QLQ-C30](#) and [QLQ-LC13](#) questionnaires.

For each of the summary scales and items measuring cough, dyspnea, and pain, the randomized treatments will be compared in terms of:

- The proportion of patients that are improved

Improvement is defined as scores that improve by at least 10 points at any time during the study. All randomized patients will be included in the denominator.

- Time to deterioration

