7. PLANNED ANALYSIS

For End-Of-Text (EoT) tables, the set of summary statistics is: N / Mean / SD / Min / Median / Max. For appendix tables, the set of summary statistics is: N / Mean / s.d. / Min / Q1 (lower quartile) / Median / Q3 (upper quartile) / Max.

Tabulations of frequencies for categorical data will include all possible categories and will display the number of observations in a category as well as the percentage (%) relative to the respective treatment group (unless otherwise specified, all patients in the respective patient set whether they have non-missing values or not). Percentages will be rounded to one decimal place. The category missing will be displayed only if there are actually missing values.

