7.5.2 Other Secondary endpoints

7.5.2.1 Best RECIST assessment

Each patient will be assigned to one of the following RECIST categories, CR, PR, SD, Non-CR/Non-PD (NN), PD or Not Evaluable (NE), irrespective of protocol violations or missing data.

Objective response is defined as CR or PR. Time to objective response is the time from randomization to the date of first documented CR or PR. The duration of objective response is the time from first documented CR or PR to the time of progression or death. Disease control is defined as CR, PR, SD or NN. The duration of disease control is the time from randomization to progression or death defined only for those patients with disease control.

Logistic regression, stratified by the same stratification factors used for the analysis of PFS, will be used to test for a difference between regimens for objective response and for disease control based on central imaging assessment. Nominal significance levels will be reported.

Time to response will be summarised by the planned imaging time points. Descriptive statistics will be calculated for the duration of objective response and duration of disease control, where applicable patients will be censored as for the PFS primary analysis.

A summary of objective response rate and disease control rate using the investigator assessment of best overall response will also be produced, along with a table comparing the investigator best overall RECIST assessment with the corresponding central imaging assessment.

The impact on objective response for each of the subgroups defined in [Section 6.4](#) will be explored. The logistic model detailed above but without the stratification factors will be used. A ‘forest plot’ will be provided presenting the odds ratio (Afatinib vs. Erlotinib) and corresponding 95% CI for each subgroup category. Subgroup analyses will only be performed on the independent central imaging assessments.

The RECIST 1.1 guidelines state that confirmation of response is not required for randomized Phase III studies that have PFS as the primary endpoint; hence the above summaries will be produced without the requirement for confirmation. However, for completeness all the above

summaries and analyses will be repeated with the requirement for confirmation, these will be considered secondary in nature.

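### The HRQoL improved/not-improved comparison is stratified by race only; leaving out the baseline score, which decides who can improve, costs some power but causes no bias

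*SAP*

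**What the plan says.** For each cough, dyspnoea and pain item or scale, SAP 7.5.2.3 sorts patients into improved, stable or worsened. Improvement is a change for the better of 10 or more points from the patient's own baseline on a 0-100 scale. Protocol 7.3.2.1.4 uses the same threshold: "Improvement is defined as scores that improve by at least 10 points at any time during the study". On the denominator the SAP says "All randomized patients will be included in the denominator". For the comparison of improving against not improving it says "A logistic regression model, stratified by stratification factor race will be used". No baseline score enters that model, and Protocol 7.3.2.1.4 names no model for this comparison, so nothing elsewhere supplies the term.

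Three neighbouring provisions matter:

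- The baseline score is collected. Flow chart footnote 9 of the protocol says the "questionnaires will be completed at baseline and then" at later courses.
- Objective response and disease control follow the same race-only rule (SAP 7.5.2.1): "Logistic regression, stratified by the same stratification factors used for the analysis of PFS".
- Tumour shrinkage is analysed "with the baseline sum of diameters fitted as a covariate" (SAP 7.5.2.2).

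For a patient with no baseline score, the SAP points two ways on tabulation. SAP 7.5.2.3 has a default, "Otherwise, a patient will be considered as stable", while the general rules of SAP 7 say "The category missing will be displayed only if there are actually missing values".

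**The concern.** The outcome is defined relative to baseline, and on these scales baseline can rule it out. A patient who reports no cough at entry cannot report 10 points less. That patient is a certain non-improver on either drug, and this is known before the first dose. A patient with no baseline score cannot be shown to have improved either. The model pools both groups with patients who can improve, which dilutes the contrast and adds avoidable variance. Objective response and disease control have no comparable baseline score that rules the outcome out.

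What is at stake is limited. A real difference in the share of patients who improve on the three focus symptoms is somewhat more likely to be missed. The type I error and the validity of the estimate are not affected. HRQoL is a non-key secondary endpoint with a supportive role (Protocol 5.3.1) and lies outside the PFS-then-OS testing order (Protocol 7.1).

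**Working it through.** **No figure to reproduce.** The documents give no effect size, improvement rate, floor share or power for this comparison.

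**Who cannot improve.** The questionnaire items have four response levels. With linear scoring to 0-100, the smallest non-zero score is 100/3 = 33.3 for one item, 100/6 = 16.7 for the two-item pain scale and 100/9 = 11.1 for the three-item dyspnoea scale. All exceed 10, so on these scales a patient is unable to improve exactly when the baseline is 0.

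**Direction, by formula.** Let q be the share able to improve and p the average improvement rate among them. Compare a test on everyone with a test on those able to improve:

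(z all / z able)² = (1 − p) / (1 − q·p), which is below 1 whenever q < 1.

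**Hand check (assumed inputs).** 400 per arm, 7% without a baseline score, 25% of the rest at 0, full follow-up, and 31.1% versus 38.0% improved.

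- Able to improve: q = 0.93 × 0.75 = 0.6975, or 279 per arm.
- Everyone: mean rate 0.3455; z = 0.069 / √(2 × 0.3455 × 0.6545 / 400) = 2.05; power Φ(2.05 − 1.96) ≈ 54%.
- Those able to improve: 44.6% versus 54.5%, mean 0.495; z = 0.0989 / √(2 × 0.495 × 0.505 / 279) = 2.34; power Φ(2.34 − 1.96) ≈ 65%.
- Relative efficiency: (1 − 0.495) / (1 − 0.3455) = 0.77.

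If 20% have no usable follow-up, p falls to 0.8 × 0.495 = 0.396 and the ratio rises to 0.604 / 0.724 = 0.83, so the loss shrinks.

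**Simulation.** Further assumptions are a race split of 22/78%; logit(improve) = logit(0.40) + 0.015 × (baseline − 40) + log(OR) × arm; probability 0 at baseline 0, without a baseline or without follow-up; and two-sided 5%. The test is the Mantel-Haenszel score test, with strata either race or race × baseline level, and with patients unable to improve in one stratum. There were 10,000 trials per cell. Power for a single item at OR 1.5, race only → race × baseline:

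| No usable follow-up | 10% at score 0 | 25% | 40% |
|---|---|---|---|
| 0% | 66 → 73% | 53 → 65% | 41 → 56% |
| 20% | 51 → 55% | 41 → 48% | 32 → 40% |
| 30% | 43 → 46% | 36 → 41% | 28 → 33% |

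Over the single item and the two- and three-item scales, the gain is 6-14, 4-8 and 3-5 points in the three rows (taken before rounding). The relative efficiency of race only is 0.68-0.86, 0.77-0.91 and 0.81-0.93. Type I error is 4.8-5.2% for both tests.

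**Sensitivity.** Single-item gain in points at full / 20% / 30% missing follow-up:

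- OR 1.2: 2-4 / 1-2 / 1
- OR 1.8: 3-16 / 4-13 / 4-10
- OR 2.5: 0-4 / 0-7 / 1-8
- OR 1.5 with control rate 25-55% and baseline slope 0-0.03: 2-21 / 2-10 / 1-6

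A second simulation used 398 versus 397 patients, a different baseline model, 10-50% at the floor and no missing follow-up. It gave a gain of about 5 to 17 points in all 15 scenarios. With no treatment effect, the race-only odds ratio averaged 1.00.

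**The case against.** The strongest reply is that nothing here is wrong. The model adjusts for the one randomisation stratum, as the other efficacy analyses do, and no stated goal is missed because HRQoL has no power target. Time to deterioration and a growth-curve model cover the same symptoms and use more of the data. That is fair, and it is why the point is minor. Neither of those analyses, however, answers which arm has more patients who improve.

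The size is assumed, and the grid starts high: its lowest case already fixes 1 − 0.93 × 0.90 = 16% of patients as non-improvers. With 5% at the floor and 5% lacking a baseline, the gain is about 1-3 points at 20-30% missing follow-up. With 5% at the floor and none lacking a baseline it is about 0-2, and with no floor it is nil. The full-follow-up row is also optimistic. The protocol's assumed survival medians of 8.75 and 7.00 months, if exponential, imply 7-9% dead by week 4 (1 − 2^(−0.92/8.75) and 1 − 2^(−0.92/7.00)). All this stands.

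The SAP does not say outright that a patient with no baseline score enters the model as not improved. The all-randomised denominator suggests it but follows directly on the percentages. The conclusion does not depend on it: at floors of 10% or more, dropping those patients from the model makes the gain only slightly smaller.

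The tumour-shrinkage comparison is only an analogy. That model analyses the minimum sum itself, whereas baseline is already inside the definition of improvement. It shows that the SAP accepts baseline adjustment, not that it contradicts itself.

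**Conclusion.** The concern holds as a matter of efficiency. Race-only stratification leaves out a variable, already collected, that fixes the outcome for some patients. At an assumed odds ratio of 1.5, with 10-40% of patients at score 0 and 7% lacking a baseline score, adding it is worth 6-14 points of power with full follow-up and 3-8 points when 20-30% lack follow-up. The direction follows from the endpoint definition whenever some patients are at the best score. The size depends wholly on the assumed floor share, effect, control rate and missing data, and it is negligible if few patients start at 0. There is no bias, no inflation of type I error and no effect on PFS or OS. This is worth changing because it is cheap; the planned analysis is not faulty.

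**What to change.** In SAP 7.5.2.3, stratify the logistic model by race and by the baseline score of the same item or scale.

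- Use the score levels, or four to five bands with cut-points fixed in advance where a scale has many levels. For the three-item scale, four bands plus the fixed stratum lost no power (at OR 1.5 and full follow-up, 73/65/55% at floors of 10/25/40%).
- Put patients whose baseline is less than 10 points from the best possible score, and patients with no baseline score, in one stratum. This wording also covers functioning scales, where the limit is at the top.
- Use a stratum and not a missing-baseline indicator, which would predict non-improvement perfectly.
- Keep all randomised patients in the reported percentages, and say whether those without a baseline score appear as stable or missing.
- Report the race-stratified odds ratio beside the adjusted one.

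The cost is SAP wording and one strata definition, with no new data. The downside is a change of estimand. The adjusted odds ratio is conditional on baseline and concerns patients able to improve, because the fixed stratum contributes nothing to the test. In the 25% case (31.1% versus 38.0%) it is about 1.50 against 1.36 = (0.380/0.620)/(0.311/0.689). With 20% lacking follow-up it is 1.40 against 1.32. The gap reflects non-collapsibility of the odds ratio, not bias, which is why both should be shown.

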## CLINICAL TRIAL PROTOCOL SYNOPSIS

Name of company: Boehringer Ingelheim		Tabulated Trial Protocol	
Name of finished product: Giotrif® / Gilotrif®, Afatinib			
Name of active ingredient: BIBW 2992			
Protocol date: 15 Nov 2011	Trial number: 1200.125		Revision date: 24 June 2016
Title of trial:	LUX-Lung 8: A randomized, open-label Phase III trial of afatinib versus erlotinib in patients with advanced squamous cell carcinoma of the lung as second-line therapy following first-line platinum-based chemotherapy		
Co-ordinating Investigators:			
Trial sites:	Multi-center trial		
Clinical phase:	III		
Objectives:	
Primary: Compare efficacy of afatinib with erlotinib as second-line treatment for patients with squamous cell carcinoma of the lung, as measured by progression-free survival (PFS).
 
Key secondary: Compare overall survival (OS) in both treatment groups
 
Secondary: Objective response rate (ORR), disease control rate (DCR), tumour shrinkage and the assessment of Health-related Quality of Life (HRQoL) and safety in both treatment groups
		
Methodology:	Randomised, open-label, active control study comparing afatinib vs. erlotinib. Eligible patients will be randomized to receive either afatinib or erlotinib in a 1:1 ratio. Independent assessment of the primary endpoint will be completed in a treatment-blinded manner. Randomization will be stratified based on race (Eastern Asian vs. non-Eastern Asian).		
No. of patients:			
total entered:	795		
each treatment:	Afatinib: 398 Erlotinib: 397		
Diagnosis :	Patients with diagnosis of advanced NSCLC squamous or mixed histology, who have completed at least 4 cycles of platinum-based doublet chemotherapy and who are eligible to receive 2 nd line therapy.		

Proprietary confidential information.

© 2016 Boehringer Ingelheim International GmbH or one or more of its affiliated companies. All rights reserved.

This document may not - in full or in part - be passed on, reproduced, published or otherwise used without prior written permission.

Name of company: Boehringer Ingelheim		Tabulated Trial Protocol	
Name of finished product: Giotrif ® / Gilotrif ® , Afatinib			
Name of active ingredient: BIBW 2992			

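### The longitudinal HRQoL model states no baseline constraint or covariate, so under its natural reading it gives up precision that a common time-0 mean would recover

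*SAP*

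**What the plan says.** SAP 7.5.2.3 opens by stating which forms are used: "HRQOL questionnaires as measured by the EORTC QLQ-C30 and QLQ-LC13 at baseline, during treatment and follow-up will be included in the analysis". Under *Change in scores over time* the mean profile is "described by a piecewise linear model adjusted for the fixed effects race", and "The models will allow the slope to change at 8, 12, and 16 weeks". Each model has a random intercept and a random slope on time from randomisation.

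The area under the fitted curve up to the median follow-up time is divided by that time, so that "it can be interpreted as the mean HRQOL score up to the median follow-up time". The effect is then defined: "The treatment effect will be estimated as the average difference between the treatment group means scores". It comes with a 95% confidence interval, a p-value and a forest plot, first for cough, dyspnoea and pain and then for every other scale and item.

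Three things are left open: whether the arms share a mean at time 0, whether baseline is a response or a covariate, and what T is. Protocol 7.3.2.1.4 adds nothing on these. The SAP does specify baseline handling one section earlier: in 7.5.2.2 the tumour shrinkage ANCOVA is run "with the baseline sum of diameters fitted as a covariate".

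**The concern.** The heading promises a change, but the defined effect is a difference in level averaged from day of randomisation. If baseline forms are responses and each arm has its own curve, the two arms also have their own starting levels. The gap between those levels then counts towards the reported effect.

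The patient-level random intercept does not remove this. It models variation between patients around the arm mean and leaves the arm means at time 0 free.

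Randomisation makes the true time-0 difference zero, so estimating it spends information on a quantity already known. The cost falls on the symptom comparisons of a named secondary endpoint. It also recurs over many scales and items, some of which will show a baseline imbalance by chance.

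**Working it through.** **What can be reproduced.** The documents give no HRQoL sample size, standard deviation, correlation or precision figure, so there is no stated figure to reproduce. The size below is a calculation under assumptions.

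**Inputs from the documents**
- Knots at 8, 12 and 16 weeks, random intercept and slope, effect = AUC/T difference (SAP 7.5.2.3).
- Forms at baseline, at the start of courses 2, 3 and 4, then every second course, plus end of treatment and follow-up (Protocol Flow Chart, footnote 9). With 28-day courses this is weeks 0, 4, 8, 12, 20, 28 and so on.
- Randomised numbers: "Afatinib: 398 Erlotinib: 397" (Protocol Synopsis).
- Planned median PFS of 14 and 10 weeks (Protocol 7.6), used only as a proxy for dropout.

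**Assumptions:** all variance components, exponential dropout, and T.

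**Method.** For patient i, let X_i have columns 1, t, (t−8)+, (t−12)+, (t−16)+, and let Z_i be its first two columns. Then V_i = Z_i G Z_i' + σ²I, and the information in an arm is the sum of X_i' V_i⁻¹ X_i. Race is left out, since it enters both versions alike.

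Let D be the between-arm difference in AUC/T and B the model's between-arm difference at time 0. With arm-specific curves the estimate is D. Imposing a common time-0 mean sets B = 0 and gives

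D − λB, where λ = Cov(D,B)/Var(B), and Var(common) = Var(D) − Cov(D,B)²/Var(B).

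The proportion of variance saved is therefore Corr²(D,B). It cannot be negative.

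**Chance baseline difference.** With an assumed SD of 25, SE = 25 × √(1/398 + 1/397) = 1.77 points. The 95% range is ±1.96 × 1.77, about ±3.5 points.

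**Worked settings** (SD 25, dropout median 12 weeks, slope variance over 12 weeks one quarter of the intercept variance, about 398 per arm, scheduled forms only):

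| ICC | T (weeks) | SE, arm-specific | SE, common time-0 mean | Variance saved |
|---|---|---|---|---|
| 0.6 | 12 | 1.65 | 1.10 | 55% |
| 0.4 | 12 | 1.52 | 1.18 | 39% |
| 0.6 | 24 | 1.98 | 1.60 | 34% |

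In the first row, 1 − (1.10/1.65)² is about 0.55. The variance removed is 1.65² − 1.10² = 1.51, whose square root is 1.23 points. Against the baseline SE of 1.77, about 1.23/1.77 = 0.7 of a chance baseline difference carries into the estimate. Across the settings examined at this slope variance, the carried fraction was about 0.3 to 0.9.

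**Main grid** (390 per arm, intercept SD 16-22, residual SD 12-20, slope SD 0.3-0.6 per week, dropout medians 14 and 10 weeks, with or without end-of-treatment and follow-up forms):

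| T | Variance saved by a common time-0 mean |
|---|---|
| 12 weeks | about 38-78% |
| 31 weeks | about 16-65% |
| 84 weeks | about 2-23% |

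The low ends come from the noisiest corner without the extra forms: intercept SD 16, residual SD 20, ICC = 256/656 = 0.39. The high ends depend a little on where the end-of-treatment and follow-up forms are placed. In the most favourable corner (intercept SD 22, residual SD 12, ICC = 484/628 = 0.77) they can reach 81%, 70% and 27%.

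A wider grid (ICC 0.3-0.8, T 12-32 weeks, several dropout and slope settings) ran from 3% to 85%. The saving was positive in every setting.

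**The case against.** The strongest reply is that separate arm intercepts are not written. The SAP lists no treatment terms at all. A common intercept with arm-specific slopes fits its words, and the loss would then be zero. The sentence that includes baseline forms introduces all the patient-reported analyses, so it does not by itself make baseline a response in this model. This stands: the separate-intercept reading is natural but inferred. The SAP does, however, name its adjustment without mentioning baseline, and it names baseline where it uses it for tumour shrinkage.

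A reader might infer that a pre-treatment difference will be reported as a false drug effect. The documents do not support that. Under randomisation the arm-specific estimator is unbiased, and its interval and p-value already allow for chance imbalance. What remains is bias conditional on the observed imbalance, and avoidable variance.

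A reader might also infer that more than half the precision is lost. That is not general. It needs high within-patient correlation, a short T and little slope variation. T is undefined: the planned median survival times of 7.00 and 8.75 months (Protocol 7.6) are about 30 and 38 weeks, and median follow-up could be longer, depending on how it is defined. At 84 weeks the gain is small.

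Finally, Protocol 5.3.1 treats the patient perspective as supportive, and HRQoL lies outside the sequence that tests PFS and then OS. The other two comparisons, responder status and time to deterioration, are already defined against each patient's own baseline. All of this limits the consequence. None of it is a reason to keep the less precise model.

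**Conclusion.** The point holds as an avoidable loss of precision in a secondary analysis, together with silence on how baseline enters. It is not a finding of bias or of type I error inflation.

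If the arms have separate time-0 means, a common mean would cut the variance by about 38-78% at T = 12 weeks, 16-65% at 31 weeks and 2-23% at 84 weeks. These ranges rest on assumed variance components and dropout, because the documents give none for HRQoL. If the sponsor already intends a common time-0 mean, nothing is lost and only the wording needs completing. The PFS and OS tests are unaffected in either case.

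**What to change.** In SAP 7.5.2.3, state that baseline scores are responses and that both arms are constrained to a common mean at time 0 (a constrained longitudinal model), keeping race and the two random effects. Report the AUC/T difference from that model. With no time-0 difference, the contrast in mean score is also the contrast in mean change, which settles the mismatch with the heading.

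The alternative is to model post-baseline scores only, with the baseline score as a covariate. The SAP should then also say from which time point the area is taken. In both cases, define the median follow-up time T.

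The cost is one or two SAP sentences and one change to the model statement, with no new data.
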